Afatinib 40 mg/day (oral) is approved for the treatment of patients with advanced EGFRm+ NSCLC. Dose adjustments are recommended based on pre-defined tolerability criteria. A post-hoc analyses of the effects of afatinib dose reduction on adverse events (AEs), pharmacokinetics (PK) and PFS in the phase III LUX-Lung 3 trial showed that dose reductions occurred in 53% (122/229) of patients; the majority (86%) within the first 6 months of treatment. In patients who dose reduced, decreases in the incidences of drug-related all grade (grade \geq 3) AEs were 99.2% (20.5%) to 46.7% (4.1%) for diarrhea, 88.5% (26.2%) to 38.5% (3.3%) for rash/acne, 77.0% (12.3%) to 27.9% (0%) for stomatitis, and 44.3% (16.4%) to 36.9% (4.9%) for nail effects. Dose reductions tended to be more common in female patients, older patients, patients of Eastern Asian ethnicity, and patients with lower body weight. Dose reduction was more likely in patients with higher plasma concentrations of afatinib. On Day 43, patients who dose reduced to 30 mg \geq 4 days previously (n=38) had geometric mean plasma afatinib concentrations of 24.4 ng/mL, vs 23.7 ng/mL in patients who remained on the 40 mg dose (n=126). Median PFS was 11.3 months in patients who dose reduced during the first 6 months of treatment, vs 11.0 months in patients who did not (HR=1.25 [95% CI, 0.91–1.72]). [ASCO 2015, Yang et al, # 8073] ([P15-05676](#)).

Post-hoc analyses from LUX-Lung 3 suggest that tolerability-guided dose adjustment of afatinib is an effective measure to reduce treatment-related AEs without affecting therapeutic efficacy:

- The frequency and severity of treatment-related AEs was lower following dose reduction
- Tolerability-guided dose modification reduced the inter-patient variability of afatinib exposure, while maintaining efficacious plasma levels
- Efficacy outcomes were similar in patients who dose reduced due to AEs versus those who did not

This real-world data (RWD) study will help to understand if dose modifications are done similar as in LUX-Lung 3 trial and if the outcome on safety and effectiveness are as in trial settings.

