8. RESEARCH QUESTION AND OBJECTIVES

Research objective:

Data from real-world will help to understand if dose modifications are done similar as in LUX-Lung 3 trial and if the outcome on safety and effectiveness are as in trial settings. Furthermore, data on modified starting doses, the underlying reasons and effects on safety and outcome are needed.

Primary objective:

To assess the effects of Gi(1)otrif[®] dose modification on the frequency and severity of adverse drug reactions (ADRs), time on treatment and time to progression with Gi(1)otrif[®] in real-world setting and compare with data from LUX-Lung 3 trial in a descriptive manner.

Secondary objective:

To obtain information on frequency and reasons for a modified starting dose of Gi(1)otrif[®] in real-world setting.

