9.7 DATA ANALYSIS

9.7.1 Main analysis

All collected data will be analysed separately for patients starting with 40mg and \leq 30mg. Although due to anticipated low sample size in patients starting with \leq 30mg, it will be mainly for exploratory purpose. Baseline demographics will be analysed with descriptive statistics (N, median, mean, 25%, 75% percentile, SD) and compared descriptively between patients who have dose modifications within the first 6 months of Gi(l)otrif[®] treatment and those who do not. All the demographics, safety and efficacy data from this study in real-world setting will be compared with data from LUX-Lung 3 trial in descriptive manner.

Analysis of Safety:

[figure not shown]
Safety analysis will include all patients treated with Gi(l)otrif[®] and be descriptive in nature. Incidence and severity of ADRs according to Common Terminology Criteria for Adverse Events (CTCAE) criteria (version 4.0) ([R15-5988](#)) when available will be summarized and displayed in number/percentage. For patients who had Gi(l)otrif[®] dose modifications within the first 6 months of Gi(l)otrif[®] treatment, frequency and severity of the common ADRs pre- and post-dose modification will be analysed (\geq 40mg vs $<$ 40mg; and \geq 30mg vs $<$ 30mg). Missing or incomplete ADR dates will be imputed according to BI internal SOPs.

Analysis of Effectiveness:

Effectiveness analysis will include all patients treated with Gi(l)otrif[®]. Time on treatment is from the date of first dose of Gi(l)otrif[®] treatment to the date of last dose of Gi(l)otrif[®] treatment. Time to progression is from the date of first dose of Gi(l)otrif[®] treatment to the earliest date of documented progression (clinical, radiographic or both clinical/radiographic progression) or death. Time on treatment and time to progression will be estimated using Kaplan-Meier method, and the median along with two-sided 95% CI will be displayed (use the Greenwood's formula for estimation of standard errors). Log-rank test will be applied to compare between patients with and without dose modifications. Time on treatment and time to progression will be compared between patients who dose reduced to $<$ 40 mg within the first 6 months of Gi(l)otrif[®] treatment and those who remained on Gi(l)otrif[®] 40 mg once daily. This is in analogy to the analysis made on LUX-Lung 3 where a cut-off of 6 months was used as most dose reductions occur during this time.

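### The planned before-and-after ADR display in dose-modified patients cannot separate a dose effect from time on treatment or from the ADR that triggered the change

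*Protocol*

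**What the plan says.** The primary objective (Protocol section 8) is to assess the effects of "dose modification on the frequency and severity of adverse drug reactions (ADRs), time on treatment and time to progression". Section 9.5 regards 200 patients as enough to analyse those effects.

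Section 9.7.1 makes the safety analysis descriptive. ADRs by CTCAE grade "when available will be summarized and displayed in number/percentage". For patients modified in the first 6 months, "frequency and severity of the common ADRs pre- and post-dose modification will be analysed", using two dose cuts (at 40 mg and at 30 mg). It gives no window length, no rate per patient-time and no time term.

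The effectiveness paragraph of the same section does use unmodified patients. There, "Log-rank test will be applied to compare between patients with and without dose modifications", and "Time on treatment and time to progression will be compared between patients who dose reduced to" below 40 mg within 6 months and "those who remained on Gi(l)otrif[®] 40 mg once daily". Otherwise modified and unmodified patients are compared only on baseline demographics.

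Section 9.3.3 lists no covariates, and Annex 2 item 5.3 (exposure by time windows) is ticked No. Item 10.5 (adjustment for confounding) is ticked Yes with page 19, but section 9.7.1 describes no such method. Sections 9.9 and 9.12 do not mention time on treatment. SAP section 1 gives derived variables and date imputation, but no time-adjusted ADR method.

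**The concern.** Three things change together at a modification. The dose changes, the patient moves to later treatment time, and the ADR that prompted the change falls on the earlier side of the line. A before-and-after percentage in modified patients alone attributes all three to one contrast. Patients observed over the same treatment time on an unchanged dose are needed to separate the first from the second, and the third must be removed by rule.

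What is at stake is the reading of the primary safety objective. Section 7 already concludes, from LUX-Lung 3 figures of this kind, that dose adjustment lowers treatment-related AEs, and section 12 plans publications. Agreement with LUX-Lung 3 would not settle the matter, because the AE figures quoted there are also before-and-after figures in patients who reduced.

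**Working it through.** **1. The protocol's own figures (section 7).** 122/229 = 53.3%, as stated. 86% of 122 is about 105 reductions within 6 months. The all-grade percentages convert to whole counts over the same 122 patients:

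| ADR | Before | After | Fall (points) |
|---|---|---|---|
| Diarrhoea | 121/122 = 99.2% | 57/122 = 46.7% | 52.5 |
| Rash/acne | 108/122 = 88.5% | 47/122 = 38.5% | 50.0 |
| Stomatitis | 94/122 = 77.0% | 34/122 = 27.9% | 49.1 |
| Nail effects | 54/122 = 44.3% | 45/122 = 36.9% | 7.4 |

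The grade 3 or higher figures also match counts over 122. The reference data therefore contain no contrast with unreduced patients on AEs.

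**2. Time alone, with no dose effect.** Assumed: 80% have the ADR before modification at month T, and onset rate halves every h months. Then post = 1 − 0.2^r. With a post window equal to T, r = 2^(−T/h). With all follow-up to 11 months, r = [2^(−T/h) − 2^(−11/h)] / [1 − 2^(−T/h)].

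| h (months) | T (months) | Post, equal window | Post, to month 11 |
|---|---|---|---|
| 1 | 1.5 | 43.4% | 58.5% |
| 1 | 3 | 18.2% | 20.5% |
| 2 | 1.5 | 61.6% | 89.7% |
| 2 | 3 | 43.4% | 56.2% |
| 3 | 1.5 | 68.0% | 96.8% |
| 3 | 3 | 55.3% | 74.2% |
| no decay | 1.5 | 80.0% | 100.0% |
| no decay | 3 | 80.0% | 98.6% |

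With equal windows and decay, time alone gives falls of 12 to 62 points. With a long post window the same process can show a rise, so the direction depends on windows the plan does not set.

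**3. The trigger alone, with no dose effect and no time trend.** Assumed: constant monthly risk of a grade 3 or higher ADR of 5% or 8%, with or without variation between patients (SD 1 on the log-odds scale); dose changed after the first such ADR in months 1 to 6; 12 months observed. Before the change the proportion is 100% by construction. Afterwards it is 36% to 68%. The monthly rate goes from 0.30–0.34 to 0.05–0.17. In addition, under SAP section 1 an ADR dated only to the year of first dose is assigned to the first-dose date, unless it ended earlier, and so counts as before modification.

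**4. Escalations.** Section 9.7.1 covers modifications, and section 9.5 expects some de-escalation and escalation among patients with a modified starting dose. After an escalation the higher dose comes later, so a decline with time works against a dose effect.

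**5. Is a 40 mg comparison group available?** Section 9.5 expects 25–30% of 200 to start lower, leaving 140–150 starters on 40 mg. If LUX-Lung 3 rates apply:
- Reduced within 6 months: 140 × 0.533 × 0.86 = 64, up to 150 × 0.533 × 0.86 = 69.
- Not reduced within 6 months: 140 − 64 = 76, up to 150 − 69 = 81.
- 95% half-width for a simple difference in proportions, 1.96 × √[p(1−p)(1/n₁ + 1/n₂)]: 14.7 points (p = 30%, 69 and 81) to 16.6 points (p = 46.7%, 64 and 76).

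These are sizes before matching, so precision will be worse. A difference in change in rates is also a different quantity, so the half-width shows only the order of magnitude.

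**6. Matching on time is not enough.** The time-matched contrast was simulated with no dose effect, 145 starters on 40 mg and reductions triggered by ADRs. With the trigger counted, it still showed a spurious fall of about 57–90 points. With the trigger excluded, bias was about −2 to +7 points. These values rest on assumed trigger probabilities and onset rates.

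**The case against.** The strongest reply is that the display is openly descriptive. Annex 2 item 2.1.4 marks formal hypotheses as not applicable, and the table mirrors the LUX-Lung 3 result that the objective requires it to be set beside. That is a good reason to keep the table. It does not answer the objective, which speaks of effects.

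The plan also summarises ADRs in all treated patients and splits all data by starting dose (40 mg against 30 mg or less). Neither supplies unmodified 40 mg patients at the same treatment time, and the split is described as mainly exploratory.

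The documents are also incomplete as supplied. The SAP announces tables that are not shown, and the Protocol contents list has a blacked-out heading after 9.7.1. A time-based ADR table cannot be excluded, so the point is limited to the visible text.

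A reader might take "dose reductions occurred in 53% (122/229) of patients; the majority (86%) within the first 6 months of treatment" as evidence that ADRs decline with time. It describes when doses were reduced, not when ADRs began, and early loss of intolerant patients from the unreduced group would give the same pattern.

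**Conclusion.** The point stands in limited form: as visible, the planned analysis cannot separate dose from time since first dose or from the triggering ADR. The mechanism follows from the design and needs no assumed rates. Its size does, and none can be taken from the documents. The figures in steps 2, 3 and 6 are illustrations.

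A reader might infer that the study will overstate the benefit of reduction, or will wrongly declare a fall in some calculable share of studies. The documents support neither. Windows are undefined and escalations are included, so the net bias may go either way. No significance test on ADRs is planned, so there is no error rate to quote. Nor do the documents say that a fall will be reported without caveat. The change is a cheap improvement that affects what the primary safety objective can conclude.

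**What to change.** Keep the pre/post table for the descriptive LUX-Lung 3 comparison. Add one contrast to the SAP:

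- **Reduced group:** 40 mg starters reduced to below 40 mg at time T within 6 months.
- **Comparator:** 40 mg starters still on treatment and still on 40 mg at the same time since first dose.
- **Windows:** equal lengths before and after T, the same in both groups.
- **Exclusions:** the ADR recorded as the reason for the reduction, and any ADR with onset on the reduction date.
- **Escalations:** analysed separately.
- **Result:** difference between groups in the change in ADR rate per patient-time, all grades and grade 3 or higher, with a 95% CI, presented descriptively.

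A Poisson or GEE model with time-varying dose should not be called equivalent; it has no matching and no differencing against the period before T, so it estimates something else. State in the SAP and in section 9.9 that the uncontrolled pre/post change will not be reported as an effect of dose reduction.

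The cost is SAP wording and one added analysis. Section 9.3 already collects ADRs, dose-change dates and reasons, and start and end dates, and the SAP already handles ADR onset dates. The downsides are a wider interval, smaller groups after matching, and residual selection, because patients left on 40 mg may be more tolerant. The contrast reduces the bias but does not remove it.

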9. RESEARCH METHODS

9.1 STUDY DESIGN

This is a non-interventional, multi-country, multi-site study based on existing data from medical records of patients treated with Gi(l)otrif[®] as part of the routine treatment according to the approved label.

Key study outcomes are:

- Effects of Gi(l)otrif[®] dose reduction on frequency of ADRs, and time on treatment, time to progression
- Proportion of patients starting with modified Gi(l)otrif[®] dose and the underlying reason(s)

Data on diagnosis, gender, date of birth, ethnicity, body weight and height, Eastern Cooperative Oncology Group performance score (ECOG) ([R14-0080](#)), EGFR mutational subgroup (Del19/L858R), starting dose of Gi(l)otrif[®], start date of Gi(l)otrif[®] treatment, dose modifications with date, ADRs, concomitant medications (limited to medication for management of diarrhea, skin effects, mucositis/stomatitis as dichotomous variables (e.g. received anti-diarrhea medication yes/no), reason for dose modification of Gi(l)otrif[®], treatment duration of Gi(l)otrif[®], time to progression and type of progression (clinical, radiographic or both clinical/radiographic progression) will be collected from patients medical records by investigators.

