## 1 Methods for calculation of derived variables

Age at registration: Year of registration [patient.birthyear] – Year of birth [registration.registered\_at]

Drug-related AE: All AE with relationship to Gi(I)otrif® [ae.gilotref\_relation\_1='yes']

Time on treatment: Date of last administration [endofobservation.date] - Date of first administration of Gi(I)otrif® [baseline.date]. For patients still on treatment, time on treatment will be censored at the date of data collection.

Time to progression (TTP): First date of progression [min(endofobservation.radio\_date, endofobservation.clinic\_date)] - Date of first administration of Gi(I)otrif® [baseline.date]. Patients not known to have a progression will be censored with the date of last contact. For patients still on treatment and without progression, time to progression will be censored at the date of data collection. For patients who stopped treatment and without progression or progression date missing, time to progression will be censored on the last contact date.

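### Time to progression takes the earlier of a clinical or radiographic date, and no analysis in the visible text shows whether a dose-group difference depends on clinical-only calls

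*Protocol*

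**What the plan says.** Protocol 9.3.2.1 lists time to progression as a primary effectiveness outcome. Section 9.7.1 runs it from first dose to the "earliest date of documented progression (clinical, radiographic or both clinical/radiographic progression) or death". The SAP, section 1, derives "Time to progression (TTP): First date of progression" as the minimum of two separately stored dates, one radiographic and one clinical. Its formula does not mention death.

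Protocol 9.1 says that "type of progression (clinical, radiographic or both clinical/radiographic progression) will be collected", and 9.3 repeats the three categories.

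On the comparison, 9.7.1 says "Log-rank test will be applied to compare between patients with and without dose modifications". It adds: "Time on treatment and time to progression will be compared between patients who dose reduced to" below 40 mg in the first 6 months and those who stayed on 40 mg. The one general statement that could cover progression type is "All collected data will be analysed separately for patients starting with 40mg and" 30 mg or less. That splits by starting dose, not by dose modification.

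The visible text gives no response criteria, scan schedule or independent assessment of progression. Item 6.2 of the ENCePP checklist (Annex 2), on validity of endpoint measurement, is ticked No. Sections 9.9 and 9.12 discuss selection bias but not how progression is called.

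**The concern.** The primary objective is the effect of dose modification on this endpoint, among others. Treatment is open and, under Protocol 10.1, in the hands of the treating investigator. A clinical call of progression depends more on judgement than a scan does. Early symptomatic decline may be recorded as toxicity, which can lead to a dose reduction and place the patient in the reduced group. It may also be recorded as clinical progression, which is an event. If that judgement falls differently in the two groups, part of a difference in time to progression reflects how progression was called.

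The data to detect this will be held: two dates and a type. Without a planned look at them, a reader of the report could not tell a difference in progression from a difference in calling.

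**Working it through.** The plan states no figure to reproduce: no alpha, power or effect size, and no clinical-only share. What follows shows a range under assumptions.

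**Group sizes.** Protocol 9.5 expects 25-30% of 200 patients to start on a lower dose: 50-60 patients, leaving 140-150 at 40 mg (midpoint 145). Protocol 7 gives 122/229 reduced in LUX-Lung 3, 86% of them within 6 months: 122 × 0.86 = 104.9, and 104.9/229 = 45.8%. Applied to 145, this is about 66 reduced and 79 not reduced (assuming the LUX-Lung 3 rate carries over).

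**Assumed clinical-only shares of events**, reducers vs non-reducers: 15% vs 30%, 10% vs 20%, 10% vs 30%. The true hazard ratio (HR), reducers over non-reducers, is 1.

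**Model A, every clinical-only call is an extra event.** With equal radiographic hazard h in both groups and clinical-only share c, the total hazard is h/(1 − c). So HR = (1 − c_non-reducer)/(1 − c_reducer).

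**Model B, a clinical call brings a real progression forward.** Simulation with 4,000 runs per case: exponential times with median 11 months (Protocol 7 gives 11.3 and 11.0), 66 vs 79 patients, uniform censoring at 6-30 months, calls 1, 2 or 3 months early but never by more than half the true time. Deaths are not modelled separately.

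| Shares | Model A: composite HR | Model B: composite HR, lead 1 to 3 months | Model B: radiographic-only HR, clinical-only patients censored at the call |
|---|---|---|---|
| 15% vs 30% | 0.70/0.85 = 0.82 | 0.99 to 0.97 | 1.21 to 1.19 |
| 10% vs 20% | 0.80/0.90 = 0.89 | 0.99 to 0.98 | 1.12 to 1.11 |
| 10% vs 30% | 0.70/0.90 = 0.78 | 0.98 to 0.95 | 1.27 to 1.25 |

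Under model B the log-rank test rejected in about 5-6% of runs at a nominal two-sided 5%. Allowing for simulation error, I read the composite HR as about 0.94-1.00.

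Three things follow.

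- Only a difference between groups matters. With 30% in both, model A gives 0.70/0.70 = 1, and the simulation gave 1.00.
- The direction is open. With the shares swapped, model A gives 1/0.89 = 1.12 to 1/0.78 = 1.28.
- The two analyses fail in different places. Under model A the composite is biased, while the radiographic analysis is not, provided the extra calls are independent of radiographic progression. Under model B the composite is nearly unbiased. The radiographic analysis is then biased the other way, because patients censored at the call were about to progress.

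For scale, the LUX-Lung 3 contrast by dose reduction in Protocol 7 is HR 1.25 (95% CI 0.91-1.72).

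**The case against.** **The visible text is incomplete.** One contents entry after Protocol 9.7.1 is blacked out, and the SAP announces tables, listings and figures whose list is not in the text supplied. A reader might infer that no analysis uses the type. The documents do not support that; they support only that none is visible. This stands.

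**The mechanism is inferred.** No section says that the physician who set the dose also called progression. It is a fair reading of routine care, no more. The leading reactions in the LUX-Lung 3 dose-reduction analysis (diarrhea, rash/acne, stomatitis, nail effects) are not obviously mistaken for tumour progression. Most calls were already in the records before the study, so knowledge of the study comparison is unlikely to have shaped them. This weakens the case for a large bias but does not exclude a difference in calling.

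**The larger ratios are a worst case.** A reader might take 0.78-0.89 as the expected bias. It requires that no clinical-only call would have become a radiographic progression. Under model B almost nothing is left. The truth may lie between.

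**A radiographic-only analysis is not a neutral referee.** Protocol 9.3 ends documentation at the last dose, so a later confirming scan may never be recorded. No scan schedule is set, so radiographic dates also depend on local practice. The last column of the table shows the risk, so this analysis must not overrule the main one.

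**LUX-Lung 3.** A reader might infer that the descriptive comparison mixes a scan-based endpoint with a partly clinical one. The documents do not say how progression was assessed there, so I make no such claim.

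**Conclusion.** The point holds in a limited form. A primary outcome merges two kinds of progression call, the plan collects what separates them, and nothing visible examines whether the dose-group result depends on the merger. A difference in clinical-only calling could move that result in either direction without being noticed.

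The size cannot be derived from the documents. With the assumed shares, and more clinical-only calls in non-reducers, the no-effect HR runs from about 0.94-1.00 (calls 1-3 months early) to 0.78-0.89 (every call an extra event). The composite definition is not shown to be wrong, and no bias is shown to exist. The gap is a missing check, and adding it is a cheap improvement.

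Separately, death is an event in Protocol 9.7.1 but absent from the SAP's event formula and censoring text. The two give different endpoints.

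**What to change.** In Protocol 9.7.1 and SAP section 1:

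1. Keep the composite as the main analysis.
2. Tabulate type of progression (clinical only, radiographic only, both) by dose-modification group.
3. Pre-state a supportive analysis of radiographic progression or death for the dose-group comparison. For patients with a clinical call only, use a later radiographic date if one is recorded; otherwise censor at last contact. State that this censoring is informative and can bias the result in the opposite direction.
4. Report both results together. Describe a difference that appears in only one as sensitive to the definition of progression. Do not add a rule that lets either result cancel the other.
5. Reconcile the SAP derivation and censoring text with the protocol on death.

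If the blacked-out section or the SAP output list already contains items 2 or 3, a cross-reference is enough.

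Cost: programming, since both dates and the type are already collected. The supportive analysis will have fewer events, hence wider intervals, and may suffer from the informative censoring described above.

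### The dose-group comparison is defined in two ways, and both sort patients by later dosing while counting time from first dose, which favours dose reduction even if it has no effect

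*Protocol*

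**What the plan says.** Protocol section 9.7.1, Analysis of Effectiveness, gives two contrasts in consecutive sentences for the same two primary outcomes, time on treatment and time to progression.

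- The test: "Log-rank test will be applied to compare between patients with and without dose modifications". No window or direction is given.
- The comparison: patients reduced below 40 mg in the first 6 months against "those who remained on Gi(l)otrif[®] 40 mg once daily". The second group has no end date.

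The protocol then explains: "This is in analogy to the analysis made on LUX-Lung 3 where a cut-off of 6 months was used". Section 7 reports that earlier analysis as a median PFS of 11.3 months "in patients who dose reduced during the first 6 months of treatment, vs 11.0 months in patients who did not", with HR 1.25 (95% CI 0.91–1.72).

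The baseline tables in section 9.7.1 use a further split: "patients who have dose modifications within the first 6 months of Gi(l)otrif[®] treatment and those who do not". The effectiveness analysis is meant to cover all treated patients. Both outcomes start at first dose. The protocol gives no landmark or time-dependent term, and the SAP derives both outcomes but no dose-group variable.

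**The concern.** There are two problems.

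**Two groupings.** A p-value from any modification versus none could be printed beside medians from early reduction versus staying on 40 mg. Neither document says which grouping governs.

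**Groups set by the future.** A patient who progresses or stops in month 1 has had little chance to be reduced and will usually fall in the comparator. A patient counted as reduced has, by construction, stayed on treatment until the reduction. Timing both from first dose credits that waiting time to the reduced group. If late reducers are also left out of the comparator, it loses only patients treated for more than 6 months.

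The study asks whether reduction preserves effectiveness in routine care, as LUX-Lung 3 suggested. A method that favours reduction under no effect can produce that answer as an artefact. It can also hide a real loss.

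**Working it through.** **1. The groupings side by side, for two 40 mg starters**

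| Grouping | First reduced in month 8 | Escalated in month 2, never reduced |
|---|---|---|
| Log-rank sentence (9.7.1) | with modification | with modification |
| Comparison sentence (9.7.1), literal | neither group | neither group |
| Baseline split (9.7.1) | not modified by month 6 | modified by month 6 |
| LUX-Lung 3 contrast (section 7) | did not reduce by month 6 | did not reduce by month 6 |

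**2. The protocol's own figures (section 7)**

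- Ever reduced: 122/229 = 53.3%, stated as 53%.
- Early: 0.86 × 122 ≈ 105. Late: 122 − 105 = 17, and 17/229 = 7.4%.
- HR check: √(0.91 × 1.72) = 1.25, as stated.
- For 200 patients: 0.53 × 200 = 106 reducers, of whom 0.86 × 106 ≈ 91 are early and 15 late.
- With follow-up cut at 6–36 months, some late reductions are never observed, and late reducers fall to about 4%, or 8 of 200. The range is therefore 4–7%.

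**3. What each analysis returns when reduction does nothing**

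Simulation with true HR = 1. There is one exponential event time per patient, standing for either outcome.

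- From section 7: median 11.1 or 13.6 months; 45.6% early reducers (0.86 × 53%) and 7.4% late (0.14 × 53%).
- Assumed: early reductions at a constant hazard over 6 months or front-loaded (mean 1.5 months); no censoring or uniform follow-up; reduction unrelated to prognosis. Only reductions seen before the event or censoring count.
- Rejection rates are for a two-sided 5% log-rank test with 150 or 200 patients.

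| Analysis | HR | Medians, months | Rejection |
|---|---|---|---|
| Any modification v none | 0.5–0.7 | – | 43–99% |
| Early v never reduced (literal reading) | 0.55–0.75 | 12.5–16.2 v 6.6–11.0 | 28–96% |
| Early v not early, no landmark | 0.67–0.89 | 12.5–16.2 v 8.6–12.4 | 12–65% |
| 6-month landmark, late reducers dropped | 0.74–0.92 | – | 7–31% |
| 6-month landmark, late reducers kept | 1.00 (0.99–1.01) | – | 4–6% |
| Early reduction as time-dependent covariate | 0.99–1.00 | – | – |

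In the first three rows, almost every rejection favours the reduced group.

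**4. Separating the two mechanisms**

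Take median 13.6 months, constant reduction hazard and follow-up of 6–36 months. Guarantee time alone (early v not early) gives HR 0.691. Dropping late reducers as well gives 0.617. On the log scale, ln 0.691 / ln 0.617 = 0.370/0.483 = 77% of the bias is guarantee time.

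With front-loaded reductions and no censoring, the same ratio is ln 0.886 / ln 0.711 = 0.121/0.341 = 35%. Unlimited follow-up is not realistic here: from the first approval (12 July 2013) to the end of data collection (31 December 2016) is about 41 months. With bounded follow-up, guarantee time is the larger part.

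**The case against.** **The two sentences may be general, then specific.** The first could name the method and the second define the groups. That is possible, but the text does not say so, and the SAP has no group variable to settle it.

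**Late reducers may not be dropped at all.** A reader might infer that the plan instructs their removal. It does not. The LUX-Lung 3 analogy, the baseline split and the all-treated population all support reading remained as remained through month 6. This objection stands: the loss of late reducers, and the departure from LUX-Lung 3, depend on the literal wording. It does not remove the bias, because early versus not early without a landmark still gives 0.67–0.89.

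**The observed result may not favour reduction.** A reader might also infer that this study will make reducers look better. The documents do not support that. Reduction may be related to prognosis, and section 7 notes that it was more common in women, older patients, patients of Eastern Asian ethnicity and those of lower weight. The reported HR of 1.25, if it is reducers over non-reducers as the sentence order suggests, points the other way. The bias pushes towards reduction, but the net direction cannot be stated.

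**The study is descriptive.** No formal hypothesis is declared (Annex 2, item 2.1.4) and no decision rests on the p-value. That lowers the stakes. However, a log-rank test is specified, the primary objective is to assess effects of dose modification, and the medians are distorted as well as the test.

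**Conclusion.** The concern holds in this form. Section 9.7.1 gives two groupings for the same primary outcomes. Under no true effect, each reading returns a hazard ratio below 1: about 0.5–0.7, 0.55–0.75 or 0.67–0.89. Guarantee time is present on every reading. The exclusion of late reducers (4–7% of patients) is an added bias that applies only if the wording is taken literally. Isolated within a landmark analysis, it gives 0.74–0.92.

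The direction of the bias follows from the design. Its size rests on the assumed reduction timing and follow-up, exponential event times, and reduction unrelated to prognosis. None of these figures predicts the observed hazard ratio.

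**What to change.** In protocol section 9.7.1 and the SAP:

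1. Define one dose-group variable among patients starting on 40 mg: reduced below 40 mg within the first 6 months, or not reduced within the first 6 months. State that late reducers, and escalators who did not reduce in that window, belong to the second group.
2. Use it for the Kaplan-Meier curves, the medians and the log-rank test. Start the clock at a 6-month landmark among patients still at risk for the outcome concerned, or enter reduction as a time-dependent covariate.
3. Remove the log-rank test of patients with and without dose modifications, or label it as description only.
4. If a version timed from first dose is kept to match LUX-Lung 3, label it as subject to guarantee-time bias.

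The cost is a few sentences. Start, modification, end and progression dates are already on the data collection list in section 9.3. The landmark excludes patients with an event or censoring before month 6, so precision falls and the result applies only to those who reach month 6. The time-dependent version avoids that, but gives a hazard ratio rather than ordinary group curves and medians. Neither removes confounding.

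A separate minor clarification: patients starting on 50 mg fall in neither of the two starting-dose strata (40 mg; 30 mg or less) and should be assigned.
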